5.4. Per-protocol (PP)

The per-protocol population will include all subjects in the OAB drug-free population with no major protocol violation. See Section 8.2 for a description of major protocol deviations.

5.5. Responders

The responders population will include all subjects who respond to treatment, defined as those who achieve at least a 50% reduction in the number of UUI episodes from baseline to 48 weeks post-activation.

5.6. TENS cohort analysis

The TENS cohort analysis will consist of the ITT population except those who do not respond to the TENS protocol. Response to the TENS protocol is defined as a 30% reduction in urgency

urinary incontinence episodes or a 30% reduction in urgency episodes from baseline after 7 days of TENS.

5.7. Long-term completers

The long-term completers population will consist of all mITT subjects who attend a particular visit. This is the primary analysis population for the effectiveness and safety analyses performed at 2 and 3 years post-activation for subjects who consent to extended follow-up.

6. Sample size consideration

The study protocol specifies enrollment of up to 135 subjects, with a target of 120 subjects. The study is designed to estimate the proportion of responders. A responder is a subject who achieves a clinically meaningful level of improvement, defined as having at least a 50% improvement in the number of UUI episodes per 24 hours on a 3-day voiding diary after 48 weeks of therapy.

The performance goal for this study is to show at least a 40% response rate after 48 weeks of therapy. The primary efficacy analysis will be performed by testing the null hypothesis H_0 that the percentage responding is less than or equal to 40% against the alternative hypothesis H_1 that the percentage is greater than 40%. The test will be performed at an overall 1-sided 2.5% level of significance.

H_0 : the true percentage responding $\leq 40\%$

H_1 : the true percentage responding $> 40\%$

The study will be considered successful if the lower bound of the 2-sided 95% exact Clopper-Pearson confidence interval for the percentage responding is greater than 40%.

The study is designed to detect an improvement in the percentage responding compared with a historical percentage of 40%. The study will enroll a target of 120 subjects to ensure collection of sufficient efficacy and safety data. The study will have 80% power to detect a 13% increase in the percentage responding from 40% to 53%, 90% power to detect a 15% increase from 40%

to 55%, and 95% power to detect a 17% increase from 40% to 57%, at a 1-sided 2.5% significance level. Calculations were performed using PASS 2019, v19.0.2.

For illustration purposes, the table below shows 95% confidence intervals for various observed proportions of responders, assuming a sample size of 120. An observed proportion of responders of at least 0.50 will give a lower bound of the 2-sided 95% exact Clopper-Pearson confidence interval slightly above 0.40.

Table 2. Confidence intervals by observed proportion of responders

Sample size=120	Observed proportion of responders					
	0.5	0.55	0.6	0.7	0.8	0.9
	(0.41, 0.59)	(0.46, 0.64)	(0.51, 0.69)	(0.61, 0.78)	(0.72, 0.87)	(0.83, 0.95)

The published literature on sacral neuromodulation supports the clinical significance of a 40% responder rate. The justification for the performance goal of 40% comes from published literature for the approved third-line device for UUI—a fully-implanted neuromodulation device called “Interstim”.

The observed modified ITT responder rates in the well-cited ROSETTA study were 51% in patients who had at least 4 months of completed diaries and 52% in patients who had at least 6 months of completed diaries. The estimated lower bounds of the 95% confidence intervals are 43% and 41%, respectively [1]. Importantly, these results are not ITT. In the review of the Insite study, the Sponsor derived an ITT responder rate of 59% from the available as-treated analysis. This deduced ITT rate leads to a lower bound of the 95% confidence interval of 44% [2]. Both of these published data were measured at 6 months whereas the primary efficacy endpoint in this study is at 48 weeks. If either published study was extended to 12 months, the number of subjects responding would likely be even smaller, resulting in a lower bound at or below 40%.

7. Statistical analysis: general conventions and considerations

Descriptive and inferential statistics will be used to summarize results of Protocol G170301. Standard descriptive statistics, such as number of subjects, mean, standard deviation, quartiles, minimum, and maximum, will be calculated for continuous variables. For discrete variables, descriptive analyses will display numbers of subjects and related percentages.

All tabular presentations will display one column of results showing the single treatment regimen of this study. Medical history and adverse event summaries will display coded results using the appropriate coding dictionaries. Any partial dates in the medication and adverse event data will be imputed. See Section 13.1 for details. All presentations and statistical analyses will be generated using SAS® Version 9.4 or higher or other validated software.

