Pivotal Study of Subcutaneous Tibial Nerve Stimulation with eCoin[®] for Urgency Urinary Incontinence.

- While other device modalities are more invasive (i.e., sacral neuromodulation or botulinum toxin of the bladder) and drug therapy is fraught with poor compliance, as an investigational device, the study will only include patients who have an inadequate response to second or third line therapies.
- Some subjects may not receive clinical benefit from eCoin[™] therapy, but are to continue with follow-up until study completion even if they ask for eCoin[™] to be explanted. Some individuals who initially do not receive clinical benefit may benefit from late response and cumulative effects of treatment.
- Subjects are intended to be without pharmacological medications for overactive bladder. If the addition of medications is medically necessary as described herein, such information will be collected and reported.

3-4 Study Procedures

All subjects will be followed for 48 weeks post-activation (which is the same as 52 weeks post-implantation). A 3-day voiding diary will be collected that reports the number and type of incontinence episodes, number of micturitions; and administering questionnaires including the OABq, and PGI-I at 4, 8, 12, 24, 36, and 48 weeks post-activation.

The follow-up study visits are described in relationship to the initial activation visit occurring 4 weeks after implantation of the study device. Thus, 52 weeks post-implantation occurs at the 48 weeks post-activation visit, and 28 weeks post-implantation occurs at the 24 weeks post-activation visit. See Visit Overview 3-4-2 for exact timing of such visits. For any enrolled subject who is not activated, the same schedule will be followed as if the subject were activated.

All subjects are expected to remain free of pharmacological medications for overactive bladder, unless medically necessary, until the primary endpoint is measured at 48 weeks post-activation. Subjects who are taking pharmacologic medication at screening should be washed off OAB medications for a period of 2 weeks prior to the baseline visit.

All subjects will either be explanted after the study visit at 48 weeks post-activation, or, if they consent to extended follow up, they will be explanted shortly after their 96 week post-activation visit or their 144 week post-activation visit.

COVID-19 Considerations

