- Visit 7b (8 weeks post-activation): Second programming to make any adjustments (Time: Between 51 and 68 days from Visit 5; Visit 7b may occur on the same day as Visit 7 or about one week following Visit 7)
- Visit 8 (12 weeks post-activation): Follow-up Assessments (3-day voiding diary, adverse event assessment, concomitant medication therapy review, patient surveys including OABq, patient satisfaction, and patient global impression of improvement) (Time: Between 79 and 89 days from Visit 5)

Pivotal Study of Subcutaneous Tibial Nerve Stimulation with eCoin[®] for Urgency Urinary Incontinence.

- Visit 9 (24 weeks post-activation): Follow-up Assessments (3-day voiding diary, adverse event assessment, concomitant medication therapy review, patient surveys including OABq, patient satisfaction, and patient global impression of improvement) (Time: Between 163 and 173 days from Visit 5)
- Visit 9b (24 weeks post-activation, described elsewhere as 28 weeks post-implantation): Third programming to make any adjustments (Time: Between 163 and 180 days from Visit 5; Visit 9b can occur on the same day as Visit 9 or about one week following Visit 9)
- Visit 10 (36 weeks post-activation): Follow-up Assessments (3-day voiding diary, adverse event assessment, concomitant medication therapy review, patient surveys including OABq, patient satisfaction, and patient global impression of improvement) (Time: Between 247 and 257 days from Visit 5)
- Visit 10b (36 weeks post-activation): Fourth programming to make any adjustments (Time: Between 247 and 264 days from Visit 5; Visit 10b can occur on the same day as Visit 10 or about one week following Visit 10)
- Visit 11 (48 weeks post-activation, described elsewhere as 52 weeks post-implantation): Follow-up Assessments (3-day voiding diary, adverse event assessment, concomitant medication therapy review, patient surveys including OABq, patient satisfaction including final study questionnaire, and patient global impression of improvement) May be done remotely if necessary with consideration to COVID-19. (Time: Between 331 and 341 days from Visit 5)
- Visit 12 (For subjects who consent to extended follow up and have their device in place at 2 years) (96 weeks post-activation): Follow-up Assessments (3-day voiding diary, adverse event assessment, concomitant medication therapy review, patient surveys including OABq, patient satisfaction, and patient global impression of improvement) (Time: Between 662 and 682 days from Visit 5)

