Original Application for an Investigational Device Exemption

Pivotal Study of Subcutaneous Tibial Nerve Stimulation with eCoin[®] for Urgency Urinary Incontinence.

This open label, single-arm study will evaluate eCoin[™]'s effectiveness in reducing episodes of urgency urinary incontinence. The proportion of subjects achieving at least a 50% reduction from baseline in the number of urgency urinary incontinence episodes will be reported.

Valencia considered a controlled trial against an approved drug or placebo. Such a trial would be very difficult to blind. Recruitment to a trial comparing eCoin[™] to Interstim would be difficult because many people are unwilling to use Interstim.

Pivotal Study of Subcutaneous Tibial Nerve Stimulation with eCoin[®] for Urgency Urinary Incontinence.

3-9-3-2 Analysis Sets

Effectiveness analyses will be generated for all analysis populations described below. Safety data will be reported on all enrolled subjects who undergo a procedure for implantation of the study device

- 1) Intent-to-Treat (ITT): All enrolled subjects who undergo a procedure for implantation of eCoin[™]. This is the primary analysis population for the safety and effectiveness analyses.
- 2) Modified Intent-to-Treat (mITT). All subjects in the ITT population meeting all eligibility criteria.
- 3) OAB drug-free. All subjects in the mITT population who took no medication for OAB during the study period.
- 4) Per-protocol (PP): The subset of OAB drug-free subjects excluding all subjects with any other major protocol violation. The SAP will define major protocol deviations.
- 5) Responders: Subjects who respond to treatment, defined as those who achieve at least a 50% reduction in the number of urgency urinary incontinence episodes from baseline to 48 weeks post-activation.
- 6) TENS Cohort Analysis (TNS): The subset of ITT subjects less any patients who do not respond to the TENS protocol where response is defined as a 30% reduction in urgency urinary incontinence episodes or a 30% reduction in urgency episodes from baseline after 7 days of TENS.
- 7) Long-term Completers: All mITT subjects who attend a particular visit. This is the primary analysis population for the effectiveness and safety analyses performed at 2 and 3 years post-activation for subjects who consent to extended follow-up.

The SAP may define additional analysis sets of subjects.

3-9-3-3 Planned analyses

3-9-3-3-1 Primary Effectiveness Outcome

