2.2. Long-term follow-up study

All subjects will be allowed to consent to extended follow-up. These subjects will not be explanted at 48 weeks post-activation, and will have the option to be followed for an additional 1 to 2 years. These subjects will be explanted shortly after their 96 week post-activation visit or their 144 week post-activation visit.

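### The primary 2- and 3-year effectiveness rate covers only subjects who opted in, kept the device and attended, so it can look stable or better after response has been lost, and no full-denominator analysis is defined beside it

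*SAP*

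**What the plan says.** SAP 5.7 defines the set, "The long-term completers population will consist of all mITT subjects who attend a particular visit", and gives it the leading role: "This is the primary analysis population for the effectiveness and safety analyses performed at 2 and 3 years post-activation". Protocol 3-9-3-2 item 7 has the same definition: "Long-term Completers: All mITT subjects who attend a particular visit".

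Three steps come before membership.

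- **Opting in.** Under SAP 2.2, subjects who consent to the extension "will have the option to be followed for an additional 1 to 2 years", and "These subjects will not be explanted at 48 weeks post-activation". Without consent, explant after week 48 is the default. Protocol 3-4 sets out the two routes: "All subjects will either be explanted after the study visit at 48 weeks post-activation, or, if they consent to extended follow up", in which case explant follows the 96- or 144-week visit.
- **Device in place.** Protocol 3-4-2 restricts Visit 12: "For subjects who consent to extended follow up and have their device in place at 2 years". Visit 13 carries the same condition at 3 years.
- **Attending** the visit.

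The week-48 analysis is built differently. It uses the ITT population. A subject explanted early, other than for an MRI, counts as a non-responder, and the remaining gaps are either counted as non-response or multiply imputed (SAP 10.1, 13.2). SAP 10.2 and 10.3 carry these rules to week 24 and to the 75% and 100% improvement outcomes at weeks 24 and 48. Nothing equivalent is written for weeks 96 or 144.

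**The concern.** At week 48 an explanted subject stays in the denominator as a failure. At weeks 96 and 144 the same subject leaves both numerator and denominator. The denominator also changes from ITT to mITT.

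The trial is open label and the outcome comes from the subject's own diary, so subjects can judge their benefit while deciding whether to continue. If those who benefit less are less likely to opt in, keep the device or attend, the long-term set is enriched for responders.

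What is at stake is how durability is read. A reader who sets the 2- and 3-year rates beside the 48-week rate could not tell sustained response from the departure of non-responders.

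**Working it through.** **The plan's own figure.** The documents state no rate for 2 or 3 years. The nearest anchor is the week-48 design. SAP section 6 says that an observed 0.50 with N = 120 gives a Clopper-Pearson lower bound slightly above 0.40. This reproduces: 60/120 gives 0.407 and 59/120 gives 0.399. Sixty responders is therefore the smallest count that meets the goal at the target size, and it is the starting point below.

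**Inputs.** From the documents: N = 120 (target enrolment). Assumed, because the documents give none:

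- p = week-48 responder rate = 0.50
- a, b = proportions of week-48 responders and non-responders who opt in, keep the device and attend
- L = share of week-48 responders who later lose response = 0.25, the same whether or not they stay
- no non-responder gains response, and ITT and mITT are the same 120 subjects

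**Formulas.**

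- Attenders = N[ap + b(1 − p)]
- Attender rate = ap(1 − L) / [ap + b(1 − p)]
- Week-48 rate in the same attenders = ap / [ap + b(1 − p)]
- True rate = p(1 − L)
- Documented responders over N = ap(1 − L)

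**Results.**

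| Retention a / b | Attenders | Week-48 rate, same attenders | Later attender rate | True later rate | Documented over 120 |
|---|---|---|---|---|---|
| 80% / 30% | 48 + 18 = 66 | 48/66 = 72.7% | 36/66 = 54.5% | 45/120 = 37.5% | 36/120 = 30.0% |
| 90% / 50% | 54 + 30 = 84 | 54/84 = 64.3% | 40.5/84 = 48.2% | 37.5% | 40.5/120 = 33.8% |
| 80% / 80% | 48 + 48 = 96 | 48/96 = 50.0% | 36/96 = 37.5% | 37.5% | 36/120 = 30.0% |

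In the first row the true rate falls by 12.5 points, yet the attender rate is above the week-48 figure of 50%. In the second row it falls only slightly, so the loss is understated. In the third row retention is equal and there is no bias.

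**How much loss can be hidden.** The attender rate stays at or above 50% while L ≤ 1 − 0.5[ap + b(1 − p)]/(ap). With 80%/30% this is 1 − 0.5 × 0.55/0.40 = 31%. With 90%/50% it is 1 − 0.5 × 0.70/0.45 = 22%.

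**A second case, where those who lose response also leave.** Take 66/120 = 55% at week 48, with 10 losing response, so the true later rate is 56/120 = 46.7%. Suppose 45 of the 56 sustained responders, 4 of the 10 lost responders and 22 of the 54 non-responders attend. The attender rate is 45/71 = 63.4% (95% CI 51.1 to 74.5). With 80% attendance regardless of response it is 45/96 = 46.9%.

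**What a paired comparison would show.** In the first row, the same 66 subjects go from 72.7% to 54.5%, so the loss is visible. In the second case, the 71 attenders go from 49/71 = 69.0% to 63.4%, a fall of 5.6 points against a true 8.3. The paired change helps but does not see those who left because response was lost, so attendance by week-48 response is needed too.

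**The case against.** **The plan may already cover this.** SAP section 5 and protocol 3-9-3-2 promise effectiveness analyses in every population, which read literally includes ITT and week-48 responders at later visits. That does not settle it. Without a rule for missing 96- or 144-week data, an ITT long-term rate is undefined. SAP 10.3 places the secondary outcomes at 24 and 48 weeks, and the repeat analyses in SAP 10.4 do not name long-term completers. The fair word is unspecified, not excluded. SAP 8.1 does report long-term completers and reasons for withdrawal; only the split by week-48 response is missing.

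**The set is openly conditional.** It is called completers and confined to those who consent. There is no 96- or 144-week objective, performance goal or test, and no passage makes a durability claim. This stands, and it limits the seriousness of the point.

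**Stronger readings the documents do not support.**

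- A reader might infer that subjects choose the extension knowing their week-48 result. Neither document says when that consent is taken. Protocol 3-3-3 even gives non-responders a reason to stay, namely possible late or cumulative benefit.
- A reader might take 55% against 30% as the bias in the first illustration. The 30% also leaves out sustained responders who did not continue. The right comparison is 55% against 37.5%.
- A reader might want every explanted or lost subject counted as response not maintained. That would make failures of the default week-48 explant, a one-year-only extension (SAP 2.2) and a depleted battery, whose typical life is 2 to 4 years (protocol 3-8).

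**Explant and follow-up.** Protocol 3-8-7-2 ends participation on explant, whereas 3-3-3 speaks of continuing follow-up after a requested explant. These passages should be reconciled. Either way, Visits 12 and 13 require the device in place.

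**Conclusion.** The concern holds as a limitation of the designated primary analysis at 2 and 3 years. The population is formed by opting in, device retention and attendance. If any of these depends on response, the rate is biased upward as an estimate for the treated population, and nothing specified in the plan would reveal it.

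The structure is certain from the text; the size is not. In the worked cases the attender rate exceeds the true rate by 17 points (54.5% against 37.5%), 11 points (48.2% against 37.5%) and 17 points (63.4% against 46.7%), and by nothing under equal retention. All of these rest on assumed retention and loss, and on treating ITT and mITT as the same. SAP 2.5 reports that several ineligible subjects were implanted at one center, so the two will differ somewhat.

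A reader might infer that the pivotal result is in doubt. It is not: the week-48 success criterion uses ITT with its own explant and missing-data rules. The point is a worthwhile, inexpensive improvement to how the long-term results are reported.

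**What to change.** In SAP 5.7 and protocol 3-9-3-2 item 7, keep the attender rate as a descriptive result and require beside it, at 96 and 144 weeks:

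1. the week-48 responder rate in the same attenders, with the paired change;
2. a table of extension consent, explant (with reason) and attendance, by week-48 responder status;
3. the number of documented responders over the ITT and mITT denominators, labelled as a lower bound because non-consent, planned explant and battery depletion are not treatment failure.

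If a proportion of week-48 responders who maintained response is reported, present it as a conservative sensitivity result with a range by reason for non-attendance, and not as the sole basis for a durability claim.

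The cost is SAP and protocol wording and a few tables. No visit or procedure is added: the diary is already scheduled at Visits 12 and 13, and protocol 3-9-1 lists explantation and study termination forms. That list shows no form for extension consent, so confirm that the fact and date of consent are captured. The downside for the sponsor is a less favourable reading of the long-term figures.

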Medications for OAB are not allowed until the primary effectiveness endpoint is reached at 48 weeks post-activation, unless judged medically necessary. For the primary effectiveness outcome variable, the primary analysis will include all subjects who have taken OAB medications. OAB medication use will be reported alongside the primary analysis. The timing of OAB medications will be displayed, including duration of treatment, start and end dates, and dosage.

The following additional sensitivity analyses may be performed.

- For the primary effectiveness outcome variable at week 48, data for subjects who have taken OAB medications while on study will be considered missing and imputed assuming they had not taken any OAB medication.
- For weeks 4, 8, 12, 24, 36, and 48, 2 different sets of analyses will be performed.
 - *While on OAB medication.* Subjects will be imputed as non-responders while they are taking OAB medication.
 - *Any OAB medication.* A very conservative set of analyses will consider a subject a non-responder at every visit after she starts OAB medication.

For example, no matter what subjects write on their diaries, the “while on OAB medication” analyses will consider subjects as non-responders from week 12 through week 36 if they take OAB medication at week 12 and stop that medication at week 36. The “any OAB medication” analyses will consider such subjects non-responders from week 12 through week 48.

3-9-8 Safety Analysis

All AEs will be coded using the preferred terms described in Subsection [3-7-4 Additional Safety Profile Information](#). All AEs will be summarized by preferred term. Tabulations of general AEs, which will be provided by time point, will include the number of subjects exposed, the number of subjects with at least one AE, and the number of subjects with at least one AE by preferred term. These tabulations will be repeated for all AEs recorded as having a causal relationship to the eCoin[™] system. Tabulations of local AEs will be provided at 24 and 48 weeks after activation (28 and 52 weeks after implantation), and will include the number of subjects exposed, the number of subjects with at least one AE, and the number of subjects with at least one AE by preferred term. Separate tables will be provided, if relevant, for SAEs or events leading to withdrawal from study.

Original Application for an Investigational Device Exemption

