Table 1. Study objectives and outcome measures	4
Table 2. Confidence intervals by observed proportion of responders	9
Table 3. Variables in the multiple imputation model	23

Abbreviations

AE	adverse event
CRF	case report form
FCS	fully conditional specification
HRQoL	Health-Related Quality of Life
ITT	intent-to-treat
MedDRA	Medical Dictionary for Regulatory Activities
mITT	modified intent-to-treat
OAB	overactive bladder
OABq	Overactive Bladder Symptom Quality of Life Questionnaire
PGI-I	Patient Global Impression of Improvement Questionnaire
PP	per-protocol
PT	preferred term
PVR	post void residual
SAE	serious adverse event
SAP	statistical analysis plan
SCI	Statistics Collaborative, Inc.
SOC	system organ class
TEAE	treatment-emergent adverse event
TENS	transcutaneous electrical nerve stimulation
UUI	urgency urinary incontinence

1. Introduction

This statistical analysis plan (SAP), which is based on Version 3.6 of the study protocol dated August 27, 2019, defines the methods and analyses that Valencia Technologies Corporation (henceforth, Valencia) plans to use to analyze the data from Protocol G170301. If the protocol is subsequently amended, this SAP may be amended as well. If there are minor differences between the analyses described in the protocol and the analyses in the SAP, the analyses in the SAP will prevail.

2. Investigational plan

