a. Weight, height, body mass index, temperature, pulse rate, respiratory rate, and blood pressure will be assessed at the screening visit. Only pulse rate, temperature, and blood pressure will be collected at subsequent visits. In addition, respiratory rate will be collected at visit 4 and visit 13.
b. For visits involving a 3-day diary, the diary should be completed over 3 consecutive days during the 7 days prior to each indicated visit. The site should give patients a telephone call to remind them of the diary requirement at least 3 days prior to each follow-up visit.
c. Visit 3 (Implant procedure) will assess satisfaction and impression of improvement relative to the TENS therapy. All other visits will be relative to the eCoin™ neuromodulation device.

5. Analysis populations

Effectiveness analyses will be generated for all analysis populations described below. Safety data will be reported on all enrolled subjects who undergo a procedure for implantation of the study device.

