5.1. Intent-to-Treat (ITT)

The intent-to-treat (ITT) population will consist of all enrolled subjects who undergo a procedure for implantation of eCoin™. This is the primary analysis population for the safety and effectiveness analyses.

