11.1. Adverse events

Adverse events (AEs) will be continuously monitored throughout the study. Investigators will classify each AE according to its relationship to study device (certainly, probably, possibly, unlikely, not related, or unclassified), intensity (mild, moderate, or severe), and seriousness. AEs will be coded using version 20.0 or later of the MedDRA dictionary and summarized by system organ class (SOC) and preferred term (PT). AEs will be summarized by subject, not event. All summaries will include the number of subjects who undergo a procedure for implantation of eCoin™ and the number of subjects with at least one event.

All AE presentations will summarize treatment-emergent adverse events (TEAEs), defined as AEs with onset on or after the device implantation procedure. AEs with completely missing onset date will be assumed treatment-emergent events. The ITT population will be used for all AE analyses.

The following presentations of treatment-emergent adverse events will be generated:

- All adverse events
- All adverse events related to study device (i.e., AEs classified as certainly, probably, and possibly related)
- All adverse events related to study device up to 52 weeks after implantation (the primary safety outcome)
- All adverse events related to study device up to 28 weeks after implantation (the secondary safety outcome)
- All adverse events related to study procedure
- Serious adverse events, and
- Adverse events leading to study discontinuation.

All AEs will be presented in a listing with SOC, PT, onset and resolution dates, study day relative to implantation, study day relative to device activation, seriousness, relationship to study device, relationship to study procedure, actions taken with study device, and outcome.

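### The primary population for 2- and 3-year safety is eligible subjects who attend the visit (SAP 5.7), which conflicts with the all-implanted safety rules in SAP 5, 11.1 and 2.5

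*SAP*

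**What the plan says.** The rule for the extension is in SAP 5.7 and protocol 3-9-3-2 item 7. The protocol defines the set as "All mITT subjects who attend a particular visit", and both documents call it the "primary analysis population for the effectiveness and safety analyses performed at 2 and 3 years post-activation for subjects who consent to extended follow-up".

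The general safety rules read differently:

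- SAP 5, opening paragraph: "Safety data will be reported on all enrolled subjects who undergo a procedure for implantation of the study device".
- SAP 5.1, on the ITT population: "This is the primary analysis population for the safety and effectiveness analyses". Protocol 3-9-3-2 item 1 says the same.
- SAP 11.1: "The ITT population will be used for all AE analyses". Treatment-emergent events are "defined as AEs with onset on or after the device implantation procedure", with no end date.
- SAP 2.5: enrolled subjects who turn out to be ineligible remain in the safety and efficacy analyses. Under SAP 5.2 the mITT set contains eligible subjects only.

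The only precedence rule, in SAP 1 with a counterpart in protocol 3-9-3, covers "minor differences between the analyses described in the protocol and the analyses in the SAP, the analyses in the SAP will prevail". For the tables themselves, protocol 3-9-8 states: "Tabulations of general AEs, which will be provided by time point, will include the number of subjects exposed".

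**The concern.** Two readings of the long-term safety population are possible, and one of them depends on what happened to the subject after implantation. Protocol 3-4-2 reserves Visits 12 and 13 for consenting subjects who still have the device in place at 2 and 3 years. Someone whose device was permanently removed because of an adverse event before the visit cannot attend it, and so is not in the set named as primary for safety at that visit. Implant-site infection, device failure and migration leading to explant are all among the risks listed in protocol 3-7-4-3. The study is meant to support a pre-market approval application (protocol 3-1), so it should be clear beforehand who is counted in the long-term safety summaries.

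**Working it through.** The plan gives no figure to reproduce here, so the check is a comparison of the texts, followed by two short pieces of algebra.

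**1. Who each rule counts at 2 and 3 years**

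| Subject | SAP 5.7 | SAP 5 and 11.1 |
|---|---|---|
| Eligible, consented, device in place, attends | in | in |
| Consented, permanently explanted before the visit | out | in |
| Consented, withdrew or missed the visit | out | in |
| Implanted, ineligibility not mended | out | in |
| Did not consent, explant delayed (protocol 3-8-8) | out | in |

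On the fourth row, SAP 2.5 reports that one center implanted several ineligible subjects. SAP 10.4 describes an mITT analysis that leaves out re-baselined subjects, which implies that re-baselined subjects otherwise belong to mITT. The row therefore concerns those whose violation was not corrected. The fifth row lies outside the scope of 5.7, and only SAP 11.1 covers it.

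**2. Whether any text settles the conflict**

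The precedence rule ranks the SAP over the protocol. The conflict lies inside the SAP (5.7 against 5, 2.5 and 11.1) and again inside protocol 3-9-3-2 (item 7 against item 1 and the opening paragraph), so ranking the documents does not resolve it. The protocol text, which is later than SAP 3.0 because it carries COVID-19 provisions, still contains item 7. It mentions a SAP addendum on COVID-19, which is not among the documents. Protocol 3-9-6 describes that addendum as dealing with missing data.

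**3. Whether SAP 11.1 stops at 52 weeks**

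It does not. Two presentations carry a cut-off (28 and 52 weeks). The tables of all events, device-related events, procedure-related events, serious events and events leading to discontinuation carry none. The listing shows every event with its study day from implantation.

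**4. Direction of any difference**

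Let N be the ITT count, A the number in the 5.7 set, a the number of those with at least one event since implantation, and b the number with an event among the other N − A subjects.

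- Rate under 5.7: a/A.
- Rate under ITT: (a + b)/N.
- The ITT rate is the higher one exactly when b/(N − A) > a/A.

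The documents give no consent, attrition or late-event rates, so neither side of this inequality is known.

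**5. Why a bare ITT percentage is not enough**

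Suppose e subjects have a first event after week 52 and n subjects are still at risk then. The crude ITT percentage e/N equals (n/N) × (e/n). The documents do not give n. If n/N is assumed to lie between 0.4 and 0.8 (48 to 96 of 120, or 54 to 108 of 135), the crude figure is 0.4 to 0.8 times the percentage among those at risk. ITT is the right set, but the number or time at risk has to be shown beside it.

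**The case against.** The strongest reply is that SAP 5.7 defines its own scope (2 and 3 years, extension consenters) and that a specific rule displaces a general one. SAP 2.2 does treat the extension as a long-term follow-up study, and 5.7 must displace 5.1 for effectiveness if it is to have any use there. This reading is reasonable, and it stands as a possible intention. It is weaker for safety, because SAP 5 and SAP 11.1 are themselves specific to safety and are worded without exception. If an exception is intended, those sections need a sentence saying so.

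It can also be said that no 2- or 3-year adverse-event table is specified. SAP 11.1 names only the 28- and 52-week cut-offs, and protocol 3-9-8 does not list its time points for general events. That is correct. However, 5.7 itself refers to safety analyses at 2 and 3 years, so their population has to be settled.

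A reader might infer more than the documents support:

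- That late events would be hidden. They would not, because the open-ended ITT tables and the listing in SAP 11.1 would show them.
- That 5.7 makes the adverse-event rate look lower. Step 4 shows that this depends on rates that the documents do not give.
- That the 2- and 3-year responder rate needs a second version to match week 48, where a non-MRI explant counts as a non-response (SAP 10.1). No comparison with week 48 is planned, so a clear label is enough.
- That disposition is not tracked. SAP 8.1 already reports long-term completers, early terminations and withdrawals by reason.

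**Conclusion.** The conflict is real and appears in both documents. Followed as written, SAP 5.7 gives a primary long-term safety set selected on eligibility, attendance and a device in place, which excludes subjects explanted or withdrawn for adverse events before the visit. This is more than missing detail, because the selection is related to the safety outcome itself.

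The consequence is limited. It concerns which summary is called primary at 2 and 3 years and what denominator it carries. The events remain visible elsewhere, provided that SAP 11.1 is applied to the extension as worded. No size or direction can be stated from the documents. The week-48 primary test and the 28- and 52-week safety outcomes are untouched. The conclusion rests on the two documents alone, and the COVID-19 addendum could not be checked.

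**What to change.** - Delete 'and safety' from SAP 5.7 and from protocol 3-9-3-2 item 7.
- State that adverse events and explants after week 52 are reported on the ITT population as in SAP 11.1, cumulatively from implantation, with the number (or time) at risk shown. This also covers ineligible implanted subjects and non-consenters awaiting a delayed explant.
- Keep the completer population for 2- and 3-year effectiveness, labelled as conditional on the device being in place and on attendance.
- Add two rows to the SAP 8.1 disposition table: consented to the extension, and device in place at 96 and 144 weeks.

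A sentence declaring 5.7 an exception would also remove the contradiction, but the primary safety set would still be selected on keeping the device, so the deletion is preferable.

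The cost is two words in each document, one clarifying statement, a label and a few table rows. No new data and no change to the imputation model are needed. Long-term safety figures may look less favourable. SAP 7.3 asks for changes to be made in a revised plan before database lock; a later change would be described as exploratory.
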